5.3.2.11 Immune-Mediated Meningoencephalitis

Immune-related meningoencephalitis is an identified risk associated with the administration of atezolizumab.

Immune-related meningoencephalitis should be suspected in any patient presenting with signs or symptoms suggestive of meningitis or encephalitis, including, but not limited to, headache, neck pain, confusion, seizure, motor or sensory dysfunction, and altered or depressed level of consciousness. Encephalopathy from metabolic or electrolyte imbalances needs to be

distinguished from potential meningoencephalitis resulting from infection (bacterial, viral, or fungal) or progression of malignancy, or secondary to a paraneoplastic process.

All patients being considered for meningoencephalitis should be urgently evaluated with a CT scan and/or MRI scan of the brain to evaluate for metastasis, inflammation, or edema. If deemed safe by the treating physician, a lumbar puncture should be performed and a neurologist should be consulted.

Patients with signs and symptoms of meningoencephalitis, in the absence of an identified alternate etiology, should be treated as defined below.

Table13: Management Guidelines for Immune-Related Meningoencephalitis

Event	Management	
Immune-related meningoencephalitis,	Permanently discontinue atezolizumab and contact the principal investigator.	
all grades	Refer patient to neurologist.	
	 Initiate treatment with 1-2 mg/kg/day IV methylprednisolone or equivalent and convert to 1-2 mg/kg/day oral prednisone or equivalent upon improvement. 	
	 If event does not improve within 48 hours after initiating corticosteroids, consider adding an immunosuppressive agent. 	
	• If event resolves to Grade 1 or better, taper corticosteroids over ≥ 1 month.	

IV = intravenous.

5.3.2.12 Renal Events

Immune-related nephritis has been associated with the administration of atezolizumab.

Eligible patients must have adequate renal function, and renal function, including serum creatinine, should be monitored throughout study treatment. Patients with abnormal renal function should be evaluated and treated for other more common etiologies (including prerenal and postrenal causes, and concomitant medications such as nonsteroidal anti-inflammatory drugs). Refer the patient to a renal specialist if clinically indicated. A renal biopsy may be required to enable a definitive diagnosis and appropriate treatment. If no alternative cause of acute kidney injury is identified, patients with signs and symptoms of acute kidney injury, in the absence of an identified alternate etiology, should be treated according to the management quidelines for immune-related renal events in the table below.

Patients with signs and symptoms of nephritis, in the absence of an identified alternate etiology, should be treated according to the guidelines in table 14.

Table 14: Management guideline for renal events

Severity	Management
Grade 1	 Continue atezolizumab. Monitor kidney function, including creatinine, closely until values resolve to normal limits or to baseline values.
Grade 2	Withhold atezolizumab for up to 12 weeks after event onset. a

	 Refer patient to renal specialist. Initiate treatment with corticosteroids equivalent to 1-2 mg/kg/day oral prednisone.
	 If event resolves to Grade 1 or better, resume atezolizumab.
	 If event does not resolve to Grade 1 or better while withholding atezolizumab, permanently discontinue atezolizumab and contact the principal investigator.
Grade	 Permanently discontinue atezolizumab and contact the principal investigator.
3-4	 Refer patient to renal specialist and consider renal biopsy.
	 Initiate treatment with corticosteroids equivalent to 1-2 mg/kg/day oral prednisone.
	 If event does not improve within 48 hours after initiating corticosteroids, consider adding an immunosuppressive agent.
	 If event resolves to Grade 1 or better, taper corticosteroids over >1 month

 $_{\rm a}$ Atezolizumab may be withheld for a longer period of time (i.e., > 12 weeks after event onset) to allow for corticosteroids (if initiated) to be reduced to the equivalent of \leq 10 mg/day oral prednisone. The acceptable length of the extended period of time must be agreed upon by the investigator and the Medical Monitor.

5.3.2.13 Immune-Mediated Myositis

Immune-mediated myositis has been associated with the administration of atezolizumab. Myositis or inflammatory myopathies are a group of disorders sharing the common feature of inflammatory muscle injury; dermatomyositis and polymyositis are among the most common disorders. Initial diagnosis is based on clinical (muscle weakness, muscle pain, skin rash in dermatomyositis), biochemical (serum creatine kinase/ creatine phosphokinase increase), and imaging (electromyography/MRI) features, and is confirmed with a muscle biopsy. "Patients mayinitially present with low grade nondescript symptoms including mild pain and weakness; thus,there should be a low threshold for suspicion of myositis.

Patients with possible myositis should be referred to a rheumatologist or neurologist. Patients with possible myositis should be monitored for signs of myocarditis and myasthenia gravis (bulbar symptoms such as dysphagia, dysphonia and dyspnea).

Patients with signs and symptoms of myositis, in the absence of an identified alternate etiology, should be treated according to the guidelines in Table 14.

Table 4 Management Guidelines for Immune-Mediated Myositis

Event	Management
Immune-	Continue atezolizumab.
mediated myositis, Grade 1	Refer patient to rheumatologist or neurologist.
	Initiate treatment as per institutional guidelines.

 $_{b}$ If corticosteroids have been initiated, they must be tapered over ≥ 1 month to the equivalent of ≤ 10 mg/day oral prednisone before atezolizumab can be resumed.

c Resumption of atezolizumab may be considered in patients who are deriving benefit and have fully recovered from the immune-related event. Patients can be re-challenged with atezolizumab only after approval has been documented by both the investigator (or an appropriate delegate) and the sponsor.

Immunemediated myositis, Grade 2

- Withhold atezolizumab for up to 12 weeks after event onset a and contact the principal investigator.
- Refer patient to rheumatologist or neurologist.
- · Initiate treatment as per institutional guidelines.
- Consider treatment with corticosteroids equivalent to 1–2 mg/kg/day IV methylprednisolone and convert to 1–2 mg/kg/day oral prednisone or equivalent upon improvement.
- If corticosteroids are initiated and event does not improve within 48 hours after initiating corticosteroids, consider adding an immunosuppressive agent.
- If event resolves to Grade 1 or better, resume atezolizumab. b
- If event does not resolve to Grade 1 or better while withholding atezolizumab, permanently discontinue atezolizumab and contact the principal investigator.

Immunemediated myositis, Grade 3

- Withhold atezolizumab for up to 12 weeks after event onset a and contact the principal investigator.
- Refer patient to rheumatologist or neurologist.
- Initiate treatment as per institutional guidelines. Respiratory support may be required in more severe cases.
- Initiate treatment with corticosteroids equivalent to 1–2 mg/kg/day IV methylprednisolone, or higher-dose bolus if patient is severely compromised (e.g., cardiac or respiratory symptoms, dysphagia, or weakness that severely limits mobility); convert to 1–2 mg/kg/day oral prednisone or equivalent upon improvement.
- Consider IVIG or plasmapheresis
- If event does not improve within 24 hours after initiating corticosteroids, consider adding an immunosuppressive agent.
- If event resolves to Grade 1 or better, resume atezolizumab. b
- If event does not resolve to Grade 1 or better while withholding atezolizumab, permanently discontinue atezolizumab and contact Medical Monitor.
- For recurrent events, treat as a Grade 4 event.

Immunemediated myositis, Grade 4

- Permanently discontinue atezolizumab and contact the principal investigator.
- · Refer patient to rheumatologist or neurologist.
- Initiate treatment as per institutional guidelines. Respiratory support may be required in more severe cases.
- Initiate treatment with corticosteroids equivalent to 1–2 mg/kg/day IV methylprednisolone, or higher-dose bolus if patient is severely compromised (e.g., cardiac or respiratory symptoms, dysphagia, or weakness that severely limits mobility); convert to 1–2 mg/kg/day oral prednisone or equivalent upon improvement.
- Consider IVIG or plasmapheresis
- If event does not improve within 24 hours after initiating corticosteroids, consider adding an immunosuppressive agent.

 If event resolves to Grade 1 or better, taper corticosteroids over ≥ 1 month.

IVIG: intravenous immunoglobulin.

а

- Atezolizumab may be withheld for a longer period of time (i.e., > 12 weeks after event onset) to allow for corticosteroids (if initiated) to be reduced to the equivalent of ≤ 10 mg/day oral prednisone. The acceptable length of the extended period of time must be agreed upon by the investigator and the sponsor.
- If corticosteroids have been initiated, they must be tapered over ≥ 1 month to the equivalent of ≤ 10 mg/day oral prednisone before atezolizumab can be resumed.
- c Resumption of atezolizumab may be considered in patients who are deriving benefit and have fully recovered from the immune-related event. Patients can be re-challenged with atezolizumab only after approval has been documented by both the investigator (or an appropriate delegate) and the sponsor.

5.3.2.14 Hemophagocytic Lymphohistiocytosis

Immune-mediated reactions may involve any organ system and may lead to hemophagocytic lymphohistiocytosis (HLH).

Clinical and laboratory features of severe CRS overlap with HLH, and HLH should be considered when CRS presentation is atypical or prolonged.

Patients with suspected HLH should be diagnosed according to published criteria by McClain and Eckstein (2014). A patient should be classified as having HLH if five of the following eight criteria are met:

- Fever ≥38.5°C
- Splenomegaly
- Peripheral blood cytopenia consisting of at least two of the following: Hemoglobin < 90 g/L (9 g/dL) (< 100 g/L [10 g/dL] for infants < 4 weeks old) Platelet count < 100×10^9 /L ($100,000/\mu$ L) ANC < 1.0×10^9 /L($1000/\mu$ L)
- Fasting triglycerides > 2.992 mmol/L (265 mg/dL) and/or fibrinogen < 1.5 g/L (150 mg/dL)
- Hemophagocytosis in bone marrow, spleen, lymph node, or liver
- Low or absent natural killer cell activity
- Ferritin > 500 mg/L (500 ng/mL)
- Soluble interleukin 2 (IL-2) receptor (soluble CD25) elevated ≥ 2 standard deviations above age-adjusted laboratory-specific norms

Patients with suspected HLH should be treated according to the guidelines in Table 16.

Table15: Management Guidelines for Suspected Hemophagocytic Lymphohistiocytosis

Event	Management
Suspected HLH	Permanently discontinue atezolizumab and contact the Medical Monitor.
	Consider patient referral to hematologist.
	Initiate supportive care, including intensive care monitoring if indicated per institutional guidelines.
	Consider initiation of IV corticosteroids, an immunosuppressive agent, and/or anti-cytokine therapy.
	 If event does not respond to treatment within 24 hours, contact the Medical Monitor and initiate treatment as appropriate according to published guidelines (La Rosée 2015; Schram and Berliner 2015; La Rosée et al. 2019).

If event resolves to Grade 1 or better, taper corticosteroids over 1 month.

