5.3.2.15 Systemic Immune Activation

Systemic immune activation is a rare condition characterized by an excessive immune response. Given the mechanism of action of atezolizumab, systemic immune activation is considered a potential risk for atezolizumab.

Recommendations regarding early identification and management of systemic immune activation are provided below. In the event of suspected systemic immune activation, atezolizumab should be withheld and clinical specialists (e.g., rheumatology, clinical immunology, or solid organ or hematopoietic stem cell transplant specialists) and the Medical Monitor should be consulted for additional guidance.

Early disease recognition is critical, and systemic immune activation should be suspected if, in the absence of an alternative etiology, the patient meets two or more of the following criteria:

- Hypotension that is refractory to aggressive IV fluid challenge Vasopressor support may be required.
- Respiratory distress that requires aggressive supportive care Supplemental oxygen and intubation may be required.
- Fever > 38.5°C
- Acute renal or hepatic failure
- Bleeding from coagulopathy
- Any of the following unexplained laboratory abnormalities (change from baseline): cytopenias (in two or more lineages), significant transaminitis, or coagulopathy

For patients with suspected systemic immune activation, an initial evaluation should include the following:

- · CBC with peripheral smear
- PT, PTT, fibrinogen, and D-dimer
- Ferritin
- Soluble interleukin 2 (IL-2) receptor (soluble CD25)
- Triglycerides
- AST, ALT, and direct bilirubin
- LDH
- Complete neurologic and abdominal examination (assess for hepatosplenomegaly)

Laboratory tests with normal results should be repeated frequently in patients for whom a high clinical suspicion of systemic immune activation exists. If neurologic abnormalities are present, consider cerebrospinal fluid analysis and/or an MRI of the brain. If cytopenias are present (Grade ≥ 2 in two or more lineages) or ferritin is ≥ 3000 ng/mL, the following evaluations should also be performed:

- Bone marrow biopsy and aspirate (assess for evidence of hemophagocytosis)
- Adenovirus, cytomegalovirus, Epstein-Barr virus, herpes-simplex virus, and human herpesvirus 6, 7, and 8 evaluation (for reactivated or active disease)

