Diagnostic criteria and recommended management for systemic immune activation are provided in Table 14. The diagnostic criteria apply only when alternative etiologies have been excluded. An adverse event of systemic immune activation should be reported on the Adverse Event eCRF if it meets the criteria for "consistent with systemic immune activation" or "probable systemic immune activation" as outlined in Table 14.

Table 104 Diagnostic Criteria and Recommended Management for Systemic Immune Activation

Systemic Immune Activation Diagnostic Criteria (applicable only when alternative etiologies have been excluded)				
Ma	jor Criteria		Minor Criteria	
• Fever ≥38.5°C on more than one occasion		e occasion	Splenomegaly	
 Ferritin ≥ 3000 ng/mL Cytopenias (Grade ≥ 2 in two or more 		more	Hemophagocytosis in bone marrow, spleen, or lymph nodes	
lineages) • Age-adjusted soluble interleukin-2 receptor			 Elevated γ-glutamyl transpeptidase (GGT) or liver function tests (AST, ALT, or direct bilirubin) 	
elevated by ≥2 s		•	Elevated triglycerides	
Severe (Grade ≥			Elevated LDH	
dysfunction in tw		าร	Decreased natural killer cell activity	
Decreased fibring		N4	of O atomic Language Authorities	
	1	Management	of Systemic Immune Activation	
Number of Criteria ≥4 major criteria	Diagnosis Consistent	_	Action to Be Taken tly discontinue atezolizumab.	
·	with systemic immune activation	 Consider treatment with an immunosuppressive agent (i.e., cytokine inhibitors) and IV corticosteroids (i.e., methylprednisolone 1 g once daily or equivalent, or dexamethasone ≥ 10 mg/m² once daily if neurologic abnormalities are present). Contact the principal investigator for additional recommendations. Consider HLH-2004 protocol [Henter] if there is no clinical improvement. 		
3 major criteria OR 2 major plus	Probable systemic immune activation	 Depending on clinical severity, follow guidelines for "Consistent with systemic immune activation" or "Possible systemic immune activation" diagnosis. Clinical specialists may be contacted for recommendations. 		
≥3 minor criteria	5 ".		•	
2 major plus ≤2 minor criteria	Possible systemic	Withhold a		
OR	immune		Consider treatment with IV corticosteroids.	
1 major plus	activation • C		ecialists may be contacted for additional dations.	
≥4 minor criteria	r critorio	Follow guidelines for "Consistent with systemic immune activation" diagnosis if there is no clinical improvement or if clinical worsening occurs.		

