If clinical in following a			nprovement occurs, atezolizumab may be resumed benefit-risk assessment by the principal r.	

Notes: Criteria are adapted from a Delphi Survey of 26 experts who provided helpful criteria in the positive diagnosis of hemophagocytic syndrome in adult patients [Hejblum].

Grades are based on National Cancer Institute Common Terminology Criteria for Adverse Events. These recommendations do not replace clinical judgment and are intended as suggested guidance.

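### The HLH and systemic immune activation sections (5.3.2.14 and 5.3.2.15) overlap, use different cut-offs and give conflicting atezolizumab instructions, with no statement of which governs

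*Protocol*

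**What the plan says.** Protocol section 5.3.2.14 gives a counting rule: "A patient should be classified as having HLH if five of the following eight criteria are met". One of the eight is ferritin above 500 ng/mL. Its management table applies as soon as HLH is suspected: "Permanently discontinue atezolizumab and contact the Medical Monitor". That table has no footnote or line allowing the drug to be restarted.

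Section 5.3.2.15 starts from a different instruction: "In the event of suspected systemic immune activation, atezolizumab should be withheld". Its table then sorts patients by major and minor criteria, and one major criterion is "Ferritin ≥ 3000 ng/mL". The tiers and actions are:

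- **Consistent** (4 or more major): permanent discontinuation.
- **Probable** (3 major, or 2 major plus at least 3 minor): follow the tier above or below, according to clinical severity.
- **Possible** (2 major plus at most 2 minor, or 1 major plus at least 4 minor): withhold. If there is clinical improvement, "atezolizumab may be resumed" after a benefit-risk assessment. If there is none, or the patient worsens, the actions of the top tier apply.

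The note under the table says the criteria were adapted from an expert survey on "helpful criteria in the positive diagnosis of hemophagocytic syndrome in adult patients". The table also counts hemophagocytosis as a minor criterion and points to the HLH-2004 protocol when there is no improvement. Neither section says which prevails when a patient meets both.

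**The concern.** Two adjacent sections draw on largely the same findings and reach different instructions on re-exposure to the study drug. A site that opens 5.3.2.14 stops atezolizumab for good. A site that opens 5.3.2.15 for the same patient may hold it and later restart. The toxicity is rare but can be fatal, so sites should not have to choose between the two rules unaided. Discontinuations for toxicity could also be handled differently between sites. The sample size, the error rates and the definition of the primary endpoint are not touched.

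**Working it through.** No sample-size or error-rate figure is involved, so the check sets the two rules side by side and counts criteria.

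| Item | 5.3.2.14 (HLH) | 5.3.2.15 (systemic immune activation) |
|---|---|---|
| Fever | ≥ 38.5°C | ≥ 38.5°C on more than one occasion (major) |
| Cytopenia | two of Hb < 9 g/dL, platelets < 100 × 10⁹/L, ANC < 1.0 × 10⁹/L | Grade 2 or worse in two or more lineages (major) |
| Ferritin | > 500 ng/mL | ≥ 3000 ng/mL (major) |
| Soluble IL-2 receptor | ≥ 2 SD above norm | ≥ 2 SD above norm (major) |
| Triglycerides, fibrinogen | > 265 mg/dL and/or < 1.5 g/L (one item) | triglycerides raised (minor), fibrinogen decreased (major), no limit shown |
| Splenomegaly | counts | minor |
| Hemophagocytosis | counts | minor |
| Low NK activity | counts | minor |

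Section 5.3.2.15 adds severe organ dysfunction (major), and raised liver tests and raised LDH (minor). The ferritin limits differ by 3000 / 500 = 6.

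**Patient A.** Fever of at least 38.5°C on more than one occasion, two-lineage cytopenia meeting both definitions, splenomegaly, triglycerides above 265 mg/dL, ferritin 800 to 1000 ng/mL, other listed findings absent.

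- 5.3.2.14: fever + cytopenia + splenomegaly + triglycerides + ferritin = 5 of 8. This is HLH, so permanent discontinuation.
- 5.3.2.15: fever + cytopenia = 2 major; splenomegaly + triglycerides = 2 minor. This is 'possible', so withhold, with resumption allowed.
- If the temperature exceeds 38.5°C, the fever and the unexplained two-lineage cytopenia also meet two items of the early-suspicion list in 5.3.2.15, which asks for two or more. The patient therefore enters that section on its own terms.

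**Sensitivity.** With ferritin at 3500 ng/mL the same patient has 3 major + 2 minor, which is 'probable'. With raised LDH or liver tests added at the lower ferritin, the count is 2 major + 3 minor, also 'probable'. In that tier either action can follow, depending on severity.

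**Patient B**, who needs no cytopenia grading. Repeated fever, splenomegaly, triglycerides above 265 mg/dL, marrow hemophagocytosis, low NK activity, ferritin 1000 ng/mL. This is 6 of 8 for HLH, against 1 major + 4 minor, again 'possible'. From these findings alone B meets only one early-suspicion item, so this conflict arises if the site goes straight to the table.

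**How often the rules part.** Fever was coded at three levels (none, once, repeated), ferritin at three (up to 500, between the limits, from 3000 ng/mL), and the ten other findings as present or absent. Any cytopenia was assumed to meet both definitions, which favours agreement. Of the 3 × 3 × 2¹⁰ = 9216 combinations, 4888 meet the HLH rule:

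- consistent: 1840 (1840/4888 = 37.6%), same instruction in both sections
- probable: 2603 (53.3%), either action by severity
- possible: 330 (6.8%), conflicting instructions
- no tier: 115 (2.4%), only 5.3.2.14 gives an instruction

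These are unweighted counts of combinations, not patient frequencies, and the early-suspicion list was not applied.

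**Cross-references.** Section 5.3.2.14 sends the reader to Table 16, but its own table is labelled 15, and the table labelled 16 is the Child-Pugh score in Appendix 1. Section 5.3.2.15 sends the reader to Table 14, a number carried by the renal-events table. The references therefore do not settle which table applies.

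**The case against.** The best defence is that the sections cover different conditions. They have separate headings and separate terms in the list of adverse events of special interest. The criteria in 5.3.2.15 apply only once other causes have been excluded, so a patient classified as HLH might be said to have another cause and to leave that section. This reading is possible, but the text does not state it. It also sits badly with a table that counts hemophagocytosis, derives from criteria for hemophagocytic syndrome and invokes HLH-2004.

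Second, the conflict is narrower than the two headline instructions suggest. Resumption in the 'possible' tier is permitted, not required, and depends on improvement and a benefit-risk assessment. The table calls itself suggested guidance that does not replace clinical judgment, and a permanent stop would breach neither section. All of this stands and limits the size of the problem. It does not tell a site whether restarting is allowed in a patient who also meets the HLH rule.

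Third, the general advice in 5.3.2 on life-threatening immune-related events might be thought to decide the matter. It is written for events not covered by the later subsections, and it contains both permanent discontinuation and a route to rechallenge.

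Fourth, different ferritin limits in two scoring schemes are not a contradiction in themselves. That is right. The contradiction lies in the instructions. The limits explain how one patient can score high on one list and low on the other.

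Finally, every cohort is closed to inclusions. The wording then matters only for patients still exposed to atezolizumab, whose number the protocol does not give.

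**Conclusion.** The point holds in a bounded form. The two sections conflict for suspected cases, for the 'possible' tier, and for 'probable' cases managed as 'possible'. At 4 or more major criteria they agree. Patient A shows the conflict using only limits printed in the protocol, assuming the cytopenia meets both definitions and the other listed findings are absent. How often such patients occur cannot be estimated from the document.

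Four stronger readings are not supported:

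- A reader might infer that the instructions are opposite throughout. They are not, given the agreement in the top tier.
- A reader might treat the two headings as one syndrome. The protocol's own links make overlap clear, but identity is an inference.
- A reader might infer that a 'possible' case could go unrecorded, because 5.3.2.15 asks for an eCRF entry under that term only for the two upper tiers. Section 9.2.2 already requires expedited reporting of events suggestive of HLH or of systemic inflammatory activation, with no tier attached.
- A reader might call the HLH ferritin unit wrong, since it is printed as "Ferritin > 500 mg/L (500 ng/mL" and the two values disagree. A symbol lost when the text was read from PDF is the likely cause, and the ng/mL value stands beside it.

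**What to change.** The passages must be reconciled. Either merge 5.3.2.14 and 5.3.2.15 into one algorithm with one atezolizumab instruction per diagnostic category, or keep both and state which takes precedence when a patient meets both. If HLH is meant to count as an alternative cause that removes a patient from 5.3.2.15, say so there. Correct the table numbers and references in both sections. The sponsor's safety team decides which criteria and which action apply; this review takes no view on that.

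The cost is safety wording in the next amendment and a notice to sites. No new tests are needed, because the two sections already call for these laboratory values, and the statistical design does not change.
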